## COVID-19 Statistical Analysis Plan

ATEA Pharmaceuticals  
Protocol AT-03A-001  
Page 60 of 77

START DATE	STOP DATE	ACTION
Partial	Known or ongoing	
If medication stop date < study drug start date, assign as prior;
 
If (known components of medication start date show that medication started before study drug start date) and (medication stop date <math>\geq</math> study drug start date or medication is ongoing at study drug start date), assign as concomitant;
 
If known components of medication start date show that medication started on or after study drug start date but before or on study drug end date, assign as concomitant.

	Partial	
If known components of medication stop date show that medication stopped before study drug start date, assign as prior;
 
If (known components of medication start date show that medication started before study drug start date) and (known components of medication stop date show that medication stopped on or after study drug start date), assign as concomitant;
 
If known components of medication start date show that medication started on or after study drug start date but before or on study drug end date, assign as concomitant.

	Missing, not ongoing	
Cannot be assigned as prior only;
 
If known components of medication start date show that medication started before study drug start date, assign as concomitant;
 
If known components of medication start date show that medication started on or after study drug start date but before or on study drug end date, assign as concomitant.

Missing	Known or ongoing	
If medication stop date < study drug start date, assign as prior;
 
If medication stop date <math>\geq</math> study drug start date or medication is ongoing at study drug start date, assign as concomitant.

Document: \\[REDACTED]\net\enterprise\Apps\sasdata\ASB\SAS\Atea\_Pharmaceuticals\AT-527\SAZ63631\Biostatistics\Documentation\SAPIAT-03A-001\_V1.0\_COVID\_SAP\_PA7.doc

Author: [REDACTED] Version Number: V1.0  
Version Date: 15Apr2021

Template No.: CS\_TP\_BS016 Revision 6

Reference: CS\_WI\_BS005

Effective Date: 02Dec2019

Copyright © 2009, 2010, 2012, 2016, 2018

Reference: CS\_WI\_BS005

proprietary to [REDACTED] Holdings

## COVID-19 Statistical Analysis Plan

ATEA Pharmaceuticals  
Protocol AT-03A-001

Page 61 of 77

START DATE	STOP DATE	ACTION
	Partial	If known components of medication stop date show that medication stopped before study drug start date, assign as prior; If known components of medication stop date show that medication stopped on or after study drug start date, assign as concomitant.
	Missing, not ongoing	Assign as concomitant.

Document: \\[REDACTED]\net\enterprise\Apps\sasdata\SASb\SAS\Atea\_Pharmaceuticals\AT-527\SZ\A63631\Biostatistics\Documentation\SAP\AT-03A-001\_V1.0\_COVID\_SAP\_PA7.doc  
Author: [REDACTED]

Version Number: V1.0  
Version Date: 15Apr2021

Template No.: CS\_TP\_BS016 Revision 6

Reference: CS\_WI\_BS005

Effective Date: 02Dec2019

Copyright © 2009, 2010, 2012, 2016, 2018, 2019 [REDACTED] All rights reserved. The contents of this document are confidential and proprietary to [REDACTED] Holdings Inc. and its subsidiaries. Unauthorized use, disclosure or reproduction is strictly prohibited.

## APPENDIX 2. PROGRAMMING CONVENTIONS FOR OUTPUTS

## DATES & TIMES

Depending on data available, dates and times will take the form yyyy-mm-dd hh:mm:ss.

## **SPELLING FORMAT**

English US.

## PAPER SIZE, ORIENTATION, AND MARGINS

The size of paper will be letter and the page orientation will be landscape. Margins will provide at least 1 inch (2.54 centimeters) of white space all around the page.

## FONTS

The font type 'Courier New' will be used, with a font size of 8. The font color will be black with no bolding, underlining, italics or subscripting.

## PRESENTATION OF TREATMENT GROUPS

For outputs, treatment groups will be represented as follows and in the given order:

Treatment Group	Tables and Graphs	Listings
AT-527	1	1
Placebo	2	2
Total [1]	3	n/a
Randomized, Not Treated	n/a	3
Screen Failure	n/a	4

Document: \\[REDACTED]\net\enterprise\Apps\sasdata\SASb\SAS\Atea\_Pharmaceuticals\AT-527\SAZ63631\Biostatistics\Documentation\SAPIAT-03A-001\_V1.0\_COVID\_SAP\_PA7.doc

Author: [REDACTED] Version Number: - V1.0  
Version Date: 15Apr2021

Template No.: CS\_TP\_BS016 Revision 6

Reference: CS\_WI\_BS005

Effective Date: 02Dec2019

Copyright © 2009, 2010, 2012, 2016, 2018

Reference: CS\_WI\_BS005

proprietary to [REDACTED] Holdings

## COVID-19 Statistical Analysis Plan

ATEA Pharmaceuticals  
Protocol AT-03A-001  
Page 63 of 77

[1] Not applicable for efficacy tables, safety tables and graphs.

## PRESENTATION OF NOMINAL VISITS

For outputs, analysis visits will be represented as follows and in that order:

Long Name (default)	Short Name
Screening	Scrn
Baseline	Base
Day 2	D02
Day 3	D03
...	...
Day 14	D14
1-week Follow-up	W1FU
2-week Follow-up	W2FU
7-week Follow-up	W7FU

## DESCRIPTIVE STATISTICS

If the original data has  $N$  decimal places, then the summary statistics will have the following decimal places:

- Minimum and maximum: N;
- Mean, median, lower and upper bounds of two-sided 95% CI: N + 1;
- SD and SE: N + 2

Document: \[REDACTED]\net\enterprise\Apps\sasdata\SASb\SAS\Atea\_Pharmaceuticals\AT-527\ISZA63631\Biostatistics\Documentation\SAPAT-03A-001\_V1.0\_COVID\_SAP\_PA7.doc  
Author: [REDACTED] Version Number: [REDACTED]

Template No.: CS TP BS016 Revision 6

Effective Date: 02Dec2019

Reference: CS WI BS005

Copyright © 2009, 2010, 2012, 2016, 2018

Reference: CS WI BS005

Copyright © 2000, 2003, 2006  
proprietary to [REDACTED] Holdings

Copyright © 2009, 2010, 2011, 2012, 2013. All rights reserved. The contents of this document are confidential and proprietary to [REDACTED] Holdings Inc. and its subsidiaries. Unauthorized use, disclosure or reproduction is strictly prohibited.

## PERCENTAGES

Percentages will be reported to one decimal place. Rounding will be applied, except for percentages < 0.1 but > 0.0 which will be presented as ' $< 0.1$ ' and percentages < 100.0 but >99.9 which will be presented as ' $>99.9$ '.

Where counts are zero, no percentages will appear in the output.

## P-VALUES

p-values will be reported to three decimal places. Rounding will be applied, except for the p-values  $< 0.001$  which will be presented as ' $< 0.001$ ' and p-values  $< 1.000$  but  $> 0.999$  which will be presented as ' $> 0.999$ '.

## LISTINGS

All listings will be ordered by the following (unless otherwise indicated in the output template):

- Randomized treatment group (or treatment received if it's a safety output);
- Subject ID;
- Parameter, when applicable;
- Date/Time, when applicable.
- Timepoint, when applicable

Document: \[REDACTED]\net\enterprise\Apps\sasdata\SASb\SAS\Atea\_Pharmaceuticals\AT-527\ISZA63631\Biostatistics\Documentation\SAP\AT-03A-001\_V1.0\_COVID\_SAP\_PA7.doc  
Author: \[REDACTED] Version Number: \[REDACTED]

Template No.: CS\_TB\_RS016 Revision 6

Reference: CS\_WI\_RS005

Template No.: CS\_IT\_BS  
Effective Date: 02Dec2019

Reference: CS\_WI\_BS005

Effective Date: 02 Dec 2019

Reference: CS WI BS005

Copyright © 2009, 2010, 2012, 2016, 2018, 2019 [REDACTED] All rights reserved. The contents of this document are confidential and proprietary to [REDACTED] Holdings Inc. and its subsidiaries. Unauthorized use, disclosure or reproduction is strictly prohibited.

## APPENDIX 3. LABORATORY ASSESSMENTS

### Chemistry (SI unit)

- Alkaline phosphatase (ALP) (IU/L)
- Alanine transaminase (ALT) (IU/L)
- Aspartate transaminase (AST) (IU/L)
- Total bilirubin (μmol/L)
- Direct bilirubin (μmol/L)
- Indirect bilirubin (μmol/L)
- Amylase (IU/L)
- Lipase (IU/L)
- Albumin (g/L)
- Blood urea nitrogen (BUN) (mmol/L)
- Blood urea
- Creatinine (μmol/L)
- Creatinine Clearance (mL/s)
- Troponin I, Troponin T (ng/L)
- Glucose (mmol/L)
- Total cholesterol (mmol/L)
- Triglycerides (mmol/L)
- Creatine kinase (CK) (IU/L)
- CK MB/MM/BB isoenzyme fraction
- Sodium (mmol/L)
- Potassium (mmol/L)
- Chloride (mmol/L)
- Bicarbonate (mmol/L)
- Calcium (mmol/L)
- Magnesium (mmol/L)
- N-terminal pro b-type natriuretic peptide (NT-proBNP) (ng/L)
- B-type natriuretic peptide (BNP) (ng/L)

### Hematology (SI unit)

- Hemoglobin (g/L)
- Hematocrit
- Absolute basophils count (x10E9/L)
- Absolute reticulocyte count (x10E9/L)

Document: \\[REDACTED]\net\enterprise\Apps\sasdata\SASb\SAS\Atea\_Pharmaceuticals\AT-527\SAZ\A63631\Biostatistics\Documentation\SAP\AT-03A-001\_V1.0\_COVID\_SAP\_PA7.doc

Author: [REDACTED] Version Number: V1.0

Version Date: 15Apr2021

Template No.: CS\_TP\_BS016 Revision 6

Reference: CS\_WI\_BS005

Effective Date: 02Dec2019

Copyright © 2009, 2010, 2012, 2016, 2018, 2019 [REDACTED] All rights reserved. The contents of this document are confidential and proprietary to [REDACTED] Holdings Inc. and its subsidiaries. Unauthorized use, disclosure or reproduction is strictly prohibited.

## COVID-19 Statistical Analysis Plan

ATEA Pharmaceuticals  
Protocol AT-03A-001  
Page 66 of 77

- Mean corpuscular volume (MCV) (fL)
- Red blood cells (RBC) (x10E12/L)
- White blood cell (WBC) count total (x10E9/L)
- Absolute neutrophils count (x10E9/L)
- Absolute lymphocyte count (x10E9/L)
- Absolute monocyte count (x10E9/L)
- Absolute eosinophils count (x10E9/L)
- Relative neutrophils count
- Relative lymphocyte count
- Relative monocyte count
- Relative eosinophils count
- Relative basophils count
- Relative reticulocyte count
- Platelet count (x10E9/L)

## Coagulation (SI unit)

- Prothrombin time (PT) (s)
- International normalized ratio (INR)
- D-dimer ( $\mu\text{g/L}$  DDU)

## Urinalysis (SI unit)

## Dip stick

- pH
- Specific gravity
- Color
- Appearance
- Blood
- Protein
- Glucose
- White blood cells
- Red blood cells
- Casts
- Bacteria
- Crystals

## Microscopy

- White blood cells
- Red blood cells
- Casts
- Bacteria
- Crystals

Document: \[REDACTED]\net\enterprise\Apps\sasdata\SASb\SAS\Atea\_Pharmaceuticals\AT-527\SAZ63631\Biostatistics\Documentation\SAPIAT-03A-001\_V1.0\_COVID\_SAP\_PA7.doc

Author: [REDACTED] Version Number: - V1.0  
Version Date: 15Apr2021

Template No.: CS\_TP\_BS016 Revision 6

Reference: CS\_WI\_BS005

Effective Date: 02Dec2019

Version Date: 15Apr2021

Copyright © 2009, 2010, 2012, 2016, 2018

Reference: CS\_WI\_BS005

Copyright © 2009, 2010, 2011  
Proprietary to [REDACTED] Holdings

Copyright © 2005, 2010, 2012, 2010, 2010, 2013. All rights reserved. The contents of this document are confidential and proprietary to [REDACTED] Holdings Inc. and its subsidiaries. Unauthorized use, disclosure or reproduction is strictly prohibited.

## COVID-19 Statistical Analysis Plan

ATEA Pharmaceuticals  
Protocol AT-03A-001  
Page 67 of 77

- Bilirubin
- Ketones
- Nitrite
- Urobilinogen
- Leukocyte esterase

Document: \[REDACTED]\net\enterprise\Apps\sasdata\SASB\SAS\Atea\_Pharmaceuticals\AT-527\SA63631\Biostatistics\Documentation\SAP\AT-03A-001\_V1.0\_COVID\_SAP\_PA7.d  
Author: \[REDACTED] Version Number:

Template No.: CS\_TP\_BS016 Revision 6  
Effective Date: 02Dec2019

Reference: CS WI BS005

Copyright © 2009, 2010, 2012, 2016, 2018  
proprietary to [REDACTED] Holdings Inc. and its s

Reference: CS WI BS005

Copyright © 2009, 2010, 2012, 2016, 2018, 2019 [REDACTED] All rights reserved. The contents of this document are confidential and proprietary to [REDACTED] Holdings Inc. and its subsidiaries. Unauthorized use, disclosure or reproduction is strictly prohibited.

## APPENDIX 4. DAIDS TOXICITY GRADE, VERSION 2.1

U.S. Department of Health and Human Services, National Institutes of Health, National Institute of Allergy and Infectious Diseases, Division of AIDS. Division of AIDS (DAIDS) Table for Grading the Severity of Adult and Pediatric Adverse Events, Version 2.1. [July 2017]. Available from:

<https://rsc.niaid.nih.gov/sites/default/files/daidsgradingcorrectedv21.pdf>

### Chemistry Tests:

DAIDS Term	Laboratory Test	No Event	Grade 1	Grade 2	Grade 3	Grade 4
Alkaline phosphatase, High	ALP (IU/L)	< 1.25 x ULN	1.25 to < 2.5 x ULN	2.5 to < 5.0 x ULN	5.0 to < 10.0 x ULN	≥ 10.0 x ULN
ALT, High	ALT (IU/L)	< 1.25 x ULN	1.25 to < 2.5 x ULN	2.5 to < 5.0 x ULN	5.0 to < 10.0 x ULN	≥ 10.0 x ULN
AST, High	AST (IU/L)	< 1.25 x ULN	1.25 to < 2.5 x ULN	2.5 to < 5.0 x ULN	5.0 to < 10.0 x ULN	≥ 10.0 x ULN
Total bilirubin, High	Total bilirubin (μmol/L)	< 1.1 x ULN	1.1 to < 1.6 x ULN	1.6 to < 2.6 x ULN	2.6 to < 5.0 x ULN	≥ 5.0 x ULN

Document: \\[REDACTED]\net\enterprise\Apps\sasdata\SASb\SAS\Atea\_Pharmaceuticals\AT-527\SZA63631\Biostatistics\Documentation\SAP\AT-03A-001\_SAP\_V1.0\_COVID\_SAP\_PA7.doc

Author: [REDACTED]

Version Number: V1.0

Version Date: 15Apr2021

Template No.: CS\_TP\_BS016 Revision 6

Effective Date: 02Dec2019

Reference: CS\_WI\_BS005

Copyright © 2009, 2010, 2012, 2016, 2018, 2019 [REDACTED] All rights reserved. The contents of this document are confidential and proprietary to [REDACTED] Holdings Inc. and its subsidiaries. Unauthorized use, disclosure or reproduction is strictly prohibited.

ATEA Pharmaceuticals  
Protocol AT-03A-001

Page 69 of 77

## COVID-19 Statistical Analysis Plan

DAIDS Term	Laboratory Test	No Event	Grade 1	Grade 2	Grade 3	Grade 4
Amylase, High	Amylase (IU/L)	< 1.1 x ULN	1.1 to < 1.5 x ULN	1.5 to < 3.0 x ULN	3.0 to < 5.0 x ULN	≥ 5.0 x ULN

Document: \\[REDACTED]\net\enterprise\Apps\sasdata\SASb\SAS\Atea\_Pharmaceuticals\AT-527\SZA63631\Biostatistics\Documentation\SAP\AT-03A-001\_SAP\_V1.0\_COVID\_SAP\_PA7.doc

Author: [REDACTED]

Version Number: V1.0

Version Date: 15Apr2021

Template No.: CS\_TP\_BS016 Revision 6

Effective Date: 02Dec2019

Reference: CS\_WI\_BS005

Copyright © 2009, 2010, 2012, 2016, 2018, 2019 [REDACTED] All rights reserved. The contents of this document are confidential and proprietary to [REDACTED] Holdings Inc. and its subsidiaries. Unauthorized use, disclosure or reproduction is strictly prohibited.

ATEA Pharmaceuticals  
Protocol AT-03A-001

Page 70 of 77

DAIDS Term	Laboratory Test	No Event	Grade 1	Grade 2	Grade 3	Grade 4
Lipase, High	Lipase (μkat/L)	< 1.1 x ULN	1.1 to < 1.5 x ULN	1.5 to < 3.0 x ULN	3.0 to < 5.0 x ULN	≥ 5.0 x ULN

---

Document: \\[REDACTED]\net\enterprise\Apps\sasdata\SASb\SAS\Atea\_Pharmaceuticals\AT-527\SZA63631\Biostatistics\Documentation\SAP\AT-03A-001\_SAP\_V1.0\_COVID\_SAP\_PA7.doc

Author: [REDACTED]

Version Number: V1.0

Version Date: 15Apr2021

Template No.: CS\_TP\_BS016 Revision 6

Effective Date: 02Dec2019

Reference: CS\_WI\_BS005

Copyright © 2009, 2010, 2012, 2016, 2018, 2019 [REDACTED] All rights reserved. The contents of this document are confidential and proprietary to [REDACTED] Holdings Inc. and its subsidiaries. Unauthorized use, disclosure or reproduction is strictly prohibited.

ATEA Pharmaceuticals  
Protocol AT-03A-001

Page 71 of 77

COVID-19 Statistical Analysis Plan

DAIDS Term	Laboratory Test	No Event	Grade 1	Grade 2	Grade 3	Grade 4
Albumin, Low	Albumin (g/L)	≥ LLN	30 to < LLN	≥ 20 to < 30	< 20	NA

Document: \\[REDACTED]net\enterprise\Apps\sasdata\SASb\SAS\Atea\_Pharmaceuticals\AT-527\SZA63631\Biostatistics\Documentation\SAP\AT-03A-001\_SAP\_V1.0\_COVID\_SAP\_PA7.doc

Author: [REDACTED]

Version Number: V1.0

Version Date: 15Apr2021

Template No.: CS\_TP\_BS016 Revision 6

Effective Date: 02Dec2019

Reference: CS\_WI\_BS005

Copyright © 2009, 2010, 2012, 2016, 2018, 2019 [REDACTED] All rights reserved. The contents of this document are confidential and proprietary to [REDACTED] Holdings Inc. and its subsidiaries. Unauthorized use, disclosure or reproduction is strictly prohibited.

ATEA Pharmaceuticals  
Protocol AT-03A-001

Page 72 of 77

## COVID-19 Statistical Analysis Plan

DAIDS Term	Laboratory Test	No Event	Grade 1	Grade 2	Grade 3	Grade 4
Creatinine, High	Creatinine ( $\mu$ mol/L)	Criteria for Grade 1 - 4 not met	1.1 to 1.3 x ULN	> 1.3 to 1.8 x ULN OR Increase to 1.3 to < 1.5 x participant's baseline	> 1.8 to < 3.5 x ULN OR Increase to 1.5 to < 2.0 x participant's baseline	$\geq$ 3.5 x ULN OR Increase of $\geq$ 2.0 x participant's baseline
Creatinine Clearance, Low	Creatinine Clearance (mL/s)	Criteria for Grade 2 - 4 not met	NA	< 1.5 to 1 OR 10 to < 30% decrease from participant's baseline	< 1 to 0.5 OR 30 to < 50% decrease from participant's baseline	< 0.5 OR $\geq$ 50% decrease from participant's baseline or dialysis needed *

Document: \\[REDACTED]net\enterprise\Apps\sasdata\SASb\SAS\Atea\_Pharmaceuticals\AT-527\SZA63631\Biostatistics\Documentation\SAP\AT-03A-001\_SAP\_V1.0\_COVID\_SAP\_PA7.doc

Author: [REDACTED]

Version Number: V1.0

Version Date: 15Apr2021

Template No.: CS\_TP\_BS016 Revision 6

Effective Date: 02Dec2019

Reference: CS\_WI\_BS005

Copyright © 2009, 2010, 2012, 2016, 2018, 2019 [REDACTED] All rights reserved. The contents of this document are confidential and proprietary to [REDACTED] Holdings Inc. and its subsidiaries. Unauthorized use, disclosure or reproduction is strictly prohibited.

COVID-19 Statistical Analysis Plan

ATEA Pharmaceuticals  
Protocol AT-03A-001

Page 73 of 77

DAIDS Term	Laboratory Test	No Event	Grade 1	Grade 2	Grade 3	Grade 4
Cardiac Troponin I, High	Troponin I (ng/L)	Criteria for Grade 4 not met	NA	NA	NA	Levels consistent with myocardial infarction or unstable angina as defined by the local laboratory *
Glucose Fasting, High	Glucose (mmol/L)	< 6.11	6.11 to < 6.95	6.95 to < 13.89	13.89 to < 27.75	≥ 27.75
Glucose, Low	Glucose (mmol/L)	≥ 3.55	3.05 to < 3.55	2.22 to < 3.05	1.67 to < 2.22	< 1.67
Cholesterol Fasting, High	Total cholesterol (mmol/L)	< 5.18	5.18 to < 6.19	6.19 to < 7.77	≥ 7.77	NA
Triglycerides Fasting, High	Triglycerides (mmol/L)	< 1.71	1.71 to 3.42	>3.42 to 5.7	>5.7 to 11.4	> 11.4
Creatine Kinase, High	Creatine kinase (IU/L)	< 3 x ULN	3 to < 6 x ULN	6 to < 10x ULN	10 to < 20 x ULN	≥ 20 x ULN

Document: \\[REDACTED]\net\enterprise\Apps\sasdata\SASb\SAS\Atea\_Pharmaceuticals\AT-527\SZA63631\Biostatistics\Documentation\SAP\AT-03A-001\_SAP\_V1.0\_COVID\_SAP\_PA7.doc

Author: [REDACTED]

Version Number: V1.0

Version Date: 15Apr2021

Template No.: CS\_TP\_BS016 Revision 6

Effective Date: 02Dec2019

Reference: CS\_WI\_BS005

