1.4. Risk/Benefit Assessment

The extensive non-clinical data and clinical data from HCV patients summarized above and in the [AT-527 Investigator's Brochure](#) indicate an encouraging risk-benefit expectation for AT-527 treatment of COVID-19 patients, supporting program advancement to the present Phase 2 clinical trial with an expectation of satisfactory clinical safety and appreciable antiviral activity. Non-clinical and clinical safety studies have not revealed any pattern of drug-attributable clinical adverse effects or any consistent clinically significant laboratory abnormalities related to any body system. Total daily doses in this COVID-19 study are higher than evaluated in the HCV

Protocol Number: AT-03A-001

program; however, the 5-day cumulative AT-527 dosing exposure for COVID-19 subjects is much less than the cumulative AT-527 exposures in the HCV program (8-12 weeks). Based on cumulative total dose received in the HCV program (30,800 mg for most subjects), there is a safety margin of 5.6-fold for the 5-day 550 mg BID COVID-19 treatment regimen (5,500 mg cumulative dose) and a 2.8-fold margin for the 1100 mg BID (11,000 mg cumulative dose) treatment regimen.

While *in vitro* data are consistent with AT-527 having a low potential for mitochondrial toxicity, some nucleoside analogues have been associated with this toxicity, resulting in damage to liver, muscles, heart, nerve, pancreas and other organs. Nephrotoxicity has also been associated with the use of some nucleoside analogs (e.g. tenofovir), but is not a class effect. The completed non-clinical assessments of AT-527 suggested negligible potential for mitochondrial toxicity. The active triphosphate of AT-527 did not inhibit the *in vitro* enzyme activities of human cellular DNA-dependent DNA polymerases (α , β or γ) and was poorly incorporated by human mitochondrial RNA polymerase (POLRMT), with a low efficiency that was similar to that of the triphosphate of sofosbuvir, a nucleoside analog that has been quite safe in broad use in HCV patients. Additionally, neither AT-527 nor sofosbuvir had any effect on mitochondrial integrity using cell-based assays. To date, there have been no clinical signs of adverse events (AEs) suggesting mitochondrial toxicity for AT-527 dosing, in animal toxicology studies or the clinical studies.

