### 17.3. LABORATORY EVALUATIONS (INCL. BLOOD GAS AND COAGULATION)

A serum pregnancy test will be performed at the screening visit, and urine or serum pregnancy test will be performed on Day 1 prior to the first dose and at hospital discharge or early termination. Chemistry (incl. blood gas,

Document: \[REDACTED]\net\enterprise\Apps\sasdata\SASb\SAS\Atea\_Pharmaceuticals\AT-527\SAZ\A63631\Biostatistics\Documentation\SAP\AT-03A-001\_V1.0\_COVID\_SAP\_PA7.doc  
Author: \[REDACTED] Version Number: V1.0  
Template No.: CS\_TP\_BS016 Revision 6 Version Date: 15Apr2021  
Effective Date: 02Dec2019 Reference: CS\_WI\_BS005

Copyright © 2009, 2010, 2012, 2016, 2018, 2019 \[REDACTED] All rights reserved. The contents of this document are confidential and proprietary to \[REDACTED] Holdings Inc. and its subsidiaries. Unauthorized use, disclosure or reproduction is strictly prohibited.

COVID-19 Statistical Analysis Plan

ATEA Pharmaceuticals  
Protocol AT-03A-001  
Page 50 of 77

cardiac related tests), hematology, coagulation and urinalysis will be performed as per the schedule of events (refer to protocol, Section 6.5). A list of laboratory parameters to be included in the outputs is included in [APPENDIX 3](#).

Quantitative laboratory parameters reported as “< X”, i.e. below the lower limit of quantification (BLQ) or “> X”, i.e. above the upper limit of quantification (ULQ), will be converted to X for the purpose of quantitative summaries, but will be presented as recorded, i.e. as “< X” or “> X” in the listings. Observed values will then be standardized (refer to [Section 17.3.1](#)) before being summarized and changes from baseline will be computed based on the standardized observed values.

The parameters which need clinical assessment will only be listed (Direct Bilirubin).

For hematology, only the following key parameters will be summarized: hemoglobin, hematocrit, RBC, platelets, WBC, neutrophils.

The following summaries will be provided by treatment group based on the SAF analysis set for each of chemistry, hematology, coagulation, and urinalysis laboratory parameters:

- Observed and change from baseline in Standard International (SI) units by visit (for quantitative parameters);
- Number and percentage of subjects in each laboratory parameter category by visit (for categorical parameters);

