- Shift from baseline to the worst post-baseline observed value during D1-D14 according to the DAIDS toxicity grades (for quantitative parameters with available DAIDS toxicity grades; refer to [Section 17.3.2](#))
- Listing of subjects with at least one post-baseline laboratory observed value meeting a DAIDS toxicity grade  $\geq 3$  (for quantitative parameters with available DAIDS toxicity grades; refer to [Section 17.3.2](#))
- Shifts from baseline to the maximum/minimum post-baseline observed value during D1-D14 according to normal range criteria (for quantitative parameters without DAIDS toxicity grades; refer to [Section 17.3.3](#));
- Maximum post-baseline ALT/AST observed value categorized as  $< 3 \times$  upper limit of normal (ULN),  $\geq 3$  to  $< 5 \times$  ULN,  $\geq 5$  to  $< 10 \times$  ULN or  $\geq 10$  ULN by maximum post-baseline total bilirubin (TBL) observed value categorized as  $< 2 \times$  ULN or  $\geq 2 \times$  ULN;
- Scatter plots of the maximum post-baseline observed value in ALT value by the maximum post-baseline observed value in TBL value, both expressed as multiple of ULN;
- Scatter plots of the maximum post-baseline observed value in AST value by the maximum post-baseline

Document: \\[REDACTED]\net\enterprise\Apps\sasdata\SASb\SAS\Atea\_Pharmaceuticals\AT-527\ISZA63631\Biostatistics\Documentation\SAP\AT-03A-001\_V1.0\_COVID\_SAP\_PA7.doc

Author: [REDACTED] Version Number: V1.0  
Version Date: 15Apr2021

Template No.: CS\_TP\_BS016 Revision 6

Reference: CS\_WI\_BS005

Effective Date: 02Dec2019

Copyright © 2009, 2010, 2012, 2016, 2018, 2019 [REDACTED] All rights reserved. The contents of this document are confidential and proprietary to [REDACTED] Holdings Inc. and its subsidiaries. Unauthorized use, disclosure or reproduction is strictly prohibited.

observed value in TBL value, both expressed as multiple of ULN;

- A listing of subjects with at least one post-baseline observed ALT value  $> 3 \times \text{ULN}$ , AST value  $> 3 \times \text{ULN}$  or TBL value  $\geq 2 \times \text{ULN}$  will be provided.

All laboratory data will be listed.

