### 17.3.2. DAIDS TOXICITY GRADES

Quantitative laboratory parameters with available DAIDS toxicity grades will be categorized as follows where higher grades representing a more severe toxicity (refer to APPENDIX 4 for each parameter toxicity grade criteria):

- Grade 1 (i.e., mild);

Document: \[REDACTED]\net\enterprise\Apps\sasdata\SASB\SAS\Atea\_Pharmaceuticals\AT-527\{SZA63631\}\Biostatistics\Documentation\SAP\AT-03A-001\_V1.0\_COVID\_SAP\_PA7.doc  
Author: \[REDACTED] Version Number: V1.0

Template No.: CS\_TP\_BS016 Revision 6

Effective Date: 02Dec2019

Reference: CS\_WI\_BS005

Copyright © 2009, 2010, 2012, 2016, 2018

proprietary to [REDACTED] Holdings

or reproduction is strictly prohibited.

Copyright © 2009, 2010, 2012, 2016, 2018, 2019 [REDACTED] All rights reserved. The contents of this document are confidential and proprietary to [REDACTED] Holdings Inc. and its subsidiaries. Unauthorized use, disclosure or reproduction is strictly prohibited.

- Grade 2 (i.e., moderate);
- Grade 3 (i.e., severe)
- Grade 4 (i.e., potentially life-threatening)

Although not defined in the DAIDS toxicity grading system, version 2.1, non-missing laboratory parameter results not meeting any of the 4 grades defined in the DAIDS toxicity grading system will be categorized as having a Grade 0 (No Event) for the purpose of the shift from baseline summaries.

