## COVID-19 Statistical Analysis Plan

DAIDS Term	Laboratory Test	No Event	Grade 1	Grade 2	Grade 3	Grade 4
Sodium, High	Sodium (mmol/L)	< 146	146 to < 150	150 to < 154	154 to < 160	≥ 160
Sodium, Low	Sodium (mmol/L)	≥ 135	130 to < 135	125 to < 130	121 to < 125	≤ 120
Potassium, High	Potassium (mmol/L)	< 5.6	5.6 to < 6.0	6.0 to < 6.5	6.5 to < 7.0	≥ 7.0
Potassium, Low	Potassium (mmol/L)	≥ 3.4	3.0 to < 3.4	2.5 to < 3.0	2.0 to < 2.5	< 2.0
Bicarbonate, Low	Bicarbonate (mmol/L)	≥ LLN	16.0 to < LLN	11.0 to < 16.0	8.0 to < 11.0	< 8.0
Calcium, High	Calcium (mmol/L)	< 2.65	2.65 to < 2.88	2.88 to < 3.13	3.13 to < 3.38	≥ 3.38
Calcium, Low	Calcium (mmol/L)	≥ 2.10	1.95 to < 2.10	1.75 to < 1.95	1.53 to < 1.75	< 1.53
Magnesium, Low	Magnesium (mmol/L)	≥ 0.70	0.60 to < 0.70	0.45 to < 0.60	0.30 to < 0.45	< 0.30

\*Will be determined from subject's Adverse Events page and identified by the medical team.

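### In SAP V1.0 a Troponin I rise not called infarction or unstable angina is shown as Grade 0 and left out of the normal-range shift that Troponin T receives, so it is not counted by arm in any laboratory abnormality table

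*SAP*

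**What the plan says.** Protocol Section 6.5 includes troponin, NT-proBNP and BNP among the laboratory evaluations, without naming a troponin assay. Protocol Section 8.2.5 makes the proportion of subjects with graded laboratory abnormalities a safety endpoint, graded by the DAIDS table. SAP Appendix 3 lists both Troponin I and Troponin T, and SAP Section 17.3.1 says that laboratory parameters are collected locally.

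The chemistry table in SAP Appendix 4 has a row for Troponin I and none for Troponin T. Grades 1 to 3 are marked not applicable. Grade 4 is "Levels consistent with myocardial infarction or unstable angina as defined by the local laboratory", and the no-event column reads "Criteria for Grade 4 not met". The Grade 4 cell carries an asterisk, which the footnote explains: "Will be determined from subject's Adverse Events page and identified by the medical team".

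SAP Section 17.3.2 adds that non-missing results meeting none of the four grades "will be categorized as having a Grade 0 (No Event) for the purpose of the shift from baseline summaries". SAP Section 17.3 plans a DAIDS shift for parameters with grades and a second shift "according to normal range criteria (for quantitative parameters without DAIDS toxicity grades"). It also plans a "Listing of subjects with at least one post-baseline laboratory observed value meeting a DAIDS toxicity grade" of 3 or higher, by-visit numeric summaries and a listing of all laboratory data.

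**The concern.** A scale that jumps from no event to Grade 4 has nowhere to put a moderate elevation. For most graded analytes this does not arise, because Grades 1 to 3 hold the intermediate values. For Troponin I the normal-range shift would be the natural place for them, but the eligibility condition on that table removes it.

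What is at stake is a count of affected subjects by arm. Protocol Section 1.4 says that mitochondrial toxicity has been associated with some nucleoside analogues, "resulting in damage to liver, muscles, heart, nerve, pancreas and other organs". Protocol Sections 1.1 and 5.6.2 also describe cardiac involvement in COVID-19 itself. Since either drug or disease could raise troponin, the informative comparison is how many subjects in each arm had a new elevation. As written, the categorical tables give that comparison for Troponin T and not for Troponin I, so whether an elevation is counted depends on the assay that the local laboratory runs.

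**Working it through.** No power, alpha or event count bears on this point, and the plan states no figure to reproduce. The check is to follow one result through each V1.0 output: a post-baseline troponin above ULN, normal at baseline, in a subject for whom neither infarction nor unstable angina has been called.

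| V1.0 output | Entry condition | Troponin I | Troponin T |
|---|---|---|---|
| DAIDS shift (17.3, 17.3.2) | has DAIDS grades | Grade 0 (No Event) | not included |
| Normal-range shift (17.3) | has no DAIDS grades | not included | normal to high |
| Grade 3 or higher listing (17.3) | meets Grade 3 or 4 | absent | not graded |
| By-visit observed and change (17.3) | quantitative parameter | included | included |
| Listing of all laboratory data (17.3) | none | included | included |
| TEAE tables (17.1.1) | recorded as an AE | only if recorded | only if recorded |

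Step by step for Troponin I:

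1. Grades 1 to 3 do not exist, so the value is either Grade 4 or no event.
2. Grade 4 is not derived from the number. The footnote takes it from the adverse events page and the medical team. With no such call, Section 17.3.2 assigns Grade 0.
3. The normal-range shift is limited to parameters without DAIDS grades. Troponin I has a row with a grade, so on the plain reading it is out.
4. The Grade 3 or higher listing can show Troponin I only at Grade 4, so it depends on the same call.
5. The adverse event tables do not close the gap completely. Protocol Section 7.1 says that laboratory abnormalities without clinical significance are not recorded as adverse events.

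The size can be written down but not evaluated. In one arm, let e be the subjects with a new Troponin I above ULN and g those called infarction or unstable angina among them. The DAIDS shift shows g above Grade 0, and e − g are missing from every categorical laboratory table. That difference runs from 0 (every elevation is so called) to e (none is). The documents give neither e nor g, nor which sites run which assay.

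**The case against.** The strongest reply is that the tables in question are not in the final delivery. The Changes form of 16 March 2022 lists the laboratory evaluations summary among the SAP items not presented, reuses the interim outputs, only lists Part B subjects and leaves the SAP text unamended. That stands. It limits the point to the V1.0 specification but does not make the V1.0 rule sound.

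The second reply is that the grading follows the protocol. Section 8.2.5 calls for DAIDS grades, and Appendix 4 presents the row as DAIDS version 2.1. That stands too. The choice open to the sponsor is the rule that makes the two shift tables mutually exclusive. The SAP already goes beyond DAIDS grades elsewhere: ALT, AST and total bilirubin have DAIDS rows, and Section 17.3 still adds tables and plots in multiples of ULN for them.

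Two stronger readings are tempting and are not supported. A reader might infer that the plan cannot show cardiac injury at all unless an infarct was reported. In fact:

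- Unstable angina also counts as Grade 4, and the medical team has a part in the call.
- The by-visit statistics include the maximum (SAP Section 7), and every value is listed.
- NT-proBNP and BNP have no Appendix 4 row and so enter the normal-range shift.
- Under Protocol Section 7.1, abnormalities that need intervention, affect study drug or come with signs or symptoms must be recorded as adverse events. TEAEs are counted per subject by arm, and the Changes form does not list that overall table as dropped.

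A reader might also infer that the protocol treats heart damage as a risk of the whole drug class. Section 1.4 speaks only of some nucleoside analogues. It calls the potential for mitochondrial toxicity low in vitro and negligible in the completed non-clinical assessments of AT-527, and it reports no clinical signs suggesting such toxicity.

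Finally, one could argue that Troponin I has no grade based on a measured value and so qualifies for the normal-range shift. The SAP does not say so, and one sentence would settle it.

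**Conclusion.** The point holds as a gap in the V1.0 specification. A Troponin I rise above ULN that is not called infarction or unstable angina is Grade 0 in one shift table, absent from the other and absent from the Grade 3 or higher listing, while the same finding by Troponin T is shifted and counted. What is lost is narrow: the by-arm number of subjects with such elevations, above all those judged not clinically significant, which the adverse event tables miss as well.

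The conclusion assumes that having a DAIDS row means having DAIDS grades for Section 17.3, and that the laboratory item in the Changes form covers both shift tables. Its numerical size is unknown. Its effect on the final delivery is nil unless the laboratory summary is kept for Part A, in which 81 subjects were randomized. It is a worthwhile, low-cost correction, and no efficacy conclusion depends on it.

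**What to change.** Add one sentence to SAP Section 17.3: Troponin I is included with Troponin T in the normal-range shift from baseline to maximum post-baseline value, despite its DAIDS row, and the number and percentage of subjects with a new value above ULN are reported by arm for each assay. Keep the adverse-event-based Grade 4 row in Appendix 4 as it is.

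For the final delivery, either retain this one laboratory output for Part A in the Changes form or state there that no by-arm count of troponin elevations will be available.

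The cost is one sentence and one more parameter in the shift-table program that V1.0 already requires. If the laboratory summaries stay dropped, the cost is that of producing this table for Part A. The data are already collected, and no clinical rule, visit or assessment changes.
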